9. DESCRIPTION OF OTHER PLANNED ANALYSES

No other planned analyses will be performed.

10. INTERIM ANALYSES

As stated in the protocol,

“There is no formal planned interim analysis for this clinical study. However, there is one planned interim data review with one planned final data analysis. Planned interim data review will be conducted when approximately 60 subjects have completed Visit 9 or completed the study. Data from this interim data review will be used to verify the assumptions for sample size calculation or to re-estimate the sample size. The interim analysis will be based off of the ITT subject population of available data”

According to the study protocol and the interim data review plan, an interim data review was conducted on 61 subjects of the FAS from a total 70 treated subjects: 29 subjects in

Customizable™ and 32 subjects in SOC. The incidence rate of SSC of Customizable™ was 17.2% and the incidence rate of the SOC was 3.1%. Since the calculated SSC rates from the interim data review were outside of the ranges of the sample size assumptions used for the study design, an early termination of the study was recommended due to lack of evidence to support the objectives and assumptions of the study. All enrolled subjects including subjects enrolled before and after interim data review will be included in the final analysis according to this document. In the final analysis, the type I error rate ($\alpha=0.048$) for statistical significance may be used for the primary analysis using the O'Brien-Fleming method.

Both, the interim data review plan and the interim data review results, may be included in the final clinical study report for this study.

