10.1 Sample Size Determination

The primary endpoint of this study is the incidence of SSC as defined in Section 5.7.1. The incidence rates of SSC will be compared between the treatment groups using Fisher's exact test.

A review of relevant literature shows that both Neaman and Greco reported surgical site complication rates for obese patients of 53.4% and 43.0%, which included rates of dehiscence and SSI of 12.3-15.4% and 16.9-26.0%, respectively.^{53;54} Vargo and Condé-Green reported large treatment effects of NPWT over closed incision versus the standard of care in complex abdominal wall reconstruction of 85% and 65%, respectively.^{55;56} Considering these references and the design of the current trial, a 35% rate of SSC is projected for the SOC arm, which is consistent with the clinical experience of the Investigators. Based on the primary endpoint of incidence rate of SSC, Fisher's exact test with a two-sided significance level $\alpha = 0.05$ will have approximately 80% power to detect the difference between an incidence rate of 35% in the SOC arm and an incidence rate of 8.75% in the Customizable arm (a 75% reduction) when the sample size in each arm is 44. To account for possible Subject replacement, the sample will be increased by up to 15% for a maximum total of 102 Subjects (51 in each treatment arm).

Due to the wide ranges of SSC incidence rate for the SOC group found in published literature, and no data from use of Customizable dressing for this study population, one planned interim data review will be performed to allow for an adjustment of the sample size. The total number of

treatment emergent AEs and SAEs (Section 10.6) and the SSC incidence rates (Section 10.5.1) will be calculated for each treatment group using the ITT population (Section 10.2.2). Since the purpose of the interim data review is not for any statistical comparison of effectiveness, no adjustment for multiplicity will be made in the final analysis.

Estimates in Table 8 were prepared to examine the SSC rates in the interim data review for sample size justification purposes only. The observed SSC incidence rates may be used to justify increasing the sample size up to 500 Subjects if the original sample size assumptions are incorrect.

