10.5 Effectiveness Analyses

10.5.1 Primary Effectiveness Analysis

The primary endpoint for this study is the incidence of SSC up to Visit 9, which will be computed and compared between the two treatment arm (Customizable versus SOC) based on the FAS population. The incidence rate of SSC will be calculated for each treatment arm as follows:

$$\text{SSC rate} = [\text{Number of Subjects who experienced SSC}] / [\text{FAS Population}]$$

Subjects included in the numerator for the incidence computation must have experienced SSC post surgery up to Visit 9. If a Subject has the same SSC event on multiple occasions or experience several events of SSC, the Subject will be counted only once in the numerator for the primary event and the highest intensity.

The incidence of SSC results will be presented by treatment arm and overall. The Fisher's Exact test with a two-sided significance level $\alpha = 0.05$ will be used to compare the SSC

proportions between the two treatment arms. The null and alternative hypotheses are listed below. A 95% confidence interval for the rate difference between the two treatment arms will be provided.

H_0 : *The Customizable and SOC treatment arms have equal incidence rates of SSC*
 $SSC_{CUSTOMIZABLE} = SSC_{SOC}$

H_1 : *The Customizable and SOC treatment arms have different incidence rates of SSC*
 $SSC_{CUSTOMIZABLE} \neq SSC_{SOC}$

If the incidence rate of SSC of Customizable is smaller than the incidence rate of SSC of SOC dressing (i.e. $SSC_{CUSTOMIZABLE} < SSC_{SOC}$) and the P-value from the above Fisher's Exact test is below 0.05 (i.e. P-value < 0.05), then we conclude that the incidence rate of SSCs decreased statistically significantly in Customizable compared with SOC dressing in this clinical study. As supportive analysis, the incidence of SSC will be compared using the ITT population.

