10.7 Deviations to the Study Protocol

All protocol deviations will be identified, recorded and presented in a protocol deviation log. Additionally, any major protocol deviations which increase Subject risk or impact clinical study endpoints will be identified and subsequently tabulated in summary tables. These may include but are not limited to improper consent of Subject, failure of Subject to meet all inclusion criteria and none of the exclusion criteria prior to randomization, and Subject noncompliance.

Any departure or deviation from the originally planned statistical methodologies will be documented and discussed in the SAP, which will include the statistical rationale for diverting from the originally planned statistical summaries and/or analyses.

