10.8 Interim Data Review

There is no formal planned interim analysis for this clinical study. However, there is one planned interim data review with one planned final data analysis. Planned interim data review will be conducted when approximately 60 subjects have completed Visit 9 or completed the study. Data from this interim data review will be used to verify the assumptions for sample size calculation or to re-estimate the sample size (Section 10.1). The interim analysis will be based off of the ITT subject population of available data.

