5.2 Sample Size and Power

Per the protocol, at the time of the trial design,

“A 35% rate of SSC is projected for the SOC arm, which is consistent with the clinical experience of the Investigators. Based on the primary endpoint of incidence rate of SSC, Fisher’s exact test with a two-sided significance level $\alpha = 0.05$ will have approximately 80% power to detect the difference between an incidence rate of 35% in the SOC arm and an incidence rate of 8.75% in the Customizable arm (a 75% reduction) when the sample size in each arm is 44. To account for possible Subject replacement, the sample will be increased by up to 15% for a maximum total of 102 Subjects (51 in each treatment arm).”

The study was terminated early before it reached the final planned sample size of 102 subjects. The study enrollment was stopped on Friday, June 30, 2017. The decision of early termination was made after the interim data review described in Section 10 of this document. A total of 71 subjects (36 in Customizable™, 35 in SOC) were enrolled in this study.

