5.3 Analysis Populations

The following subject populations for this clinical study are:

Safety Population – The Safety population will consist of all subjects who are randomized and do not withdraw before the attempt to apply the assigned treatment with Customizable™ or SOC surgical incision dressing regardless of its duration. Subject data will be analyzed in the arm to which they were treated. All safety results for this study will be presented based on the safety population.

Intent-to-Treat (ITT) Population – The ITT population will consist of all subjects who are randomized and do not withdraw before the attempt to apply the assigned treatment with Customizable™ or SOC surgical incision dressing regardless of its duration. Subject data will be analyzed in the arm to which they were randomized. All supportive or exploratory analyses for this study will be presented based on the ITT population.

Full Analysis Population (FAS): The FAS subject population will consist of all subjects who i) met all of the pre-operative and intra-operative inclusion criteria and none of the pre-operative and intra-operative exclusion criteria, ii) have been randomized, and iii) received treatment with either Customizable™ or SOC dressing. Subjects without SSC will need to receive at least 5 days of Customizable™ or at least 1 day of SOC dressing to be included in this set and completed Day 30 (\pm 4 days). Subjects with SSC prior to Day 30 (\pm 4 days) will be included in this set regardless of length of Customizable™ or SOC dressing treatment and treatment follow up. Subject data will be analyzed in the arm to which they were randomized and treated. The primary and secondary effectiveness analyses for this study will be based on the FAS population.

Subjects having important disqualifying protocol deviations will be excluded from ITT and/or FAS based on the results from the protocol deviation review described in Section 5.4 of this document.

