7. STATISTICAL ANALYSIS OF EFFECTIVENESS MEASURES

7.1 Primary Effectiveness Analysis

The primary endpoint will be analyzed on subjects in the Full Analysis Population. The incidence rate of SSC will be calculated for each treatment group as follows:

$$SSC\ rate = [Number\ of\ subjects\ who\ experienced\ an\ SSC] / [Full\ Analysis\ Population]$$

Subjects included in the numerator for the incidence computation must have experienced an SSC within 34 days after the initial study surgery. If a subject experiences one or more SSC events, the subject will be counted only once in the numerator. The number and percent of subjects experiencing each component of the SSC (dehiscence, superficial SSI, deep SSI, or any SSI) will also be presented.

The incidence rates of SSC results will be presented by treatment group and overall. The Fisher's Exact test with a 2-sided significant level $\alpha = 0.048$ will be used to compare the SSC incidence rates between two treatment groups. The null and alternative hypotheses are as the follows:

H₀: The Customizable™ and SOC treatment groups have equal incidence rates of SSC

$$SSC_{Customizable} = SSC_{SOC}$$

H₁: The Customizable™ and SOC treatment groups have different incidence rates of SSC

$$SSC_{Customizable} \neq SSC_{SOC}$$

If the incidence rate of SSC of Customizable™ is smaller than the incidence rate of SSC of SOC dressing (i.e. $SSC_{Customizable} < SSC_{SOC}$) and the P-value from the above Fisher's Exact test is below 0.048 (i.e. $P\text{-value} \leq 0.048$) then we conclude that the incidence rate of SSCs decreased statistically significantly in Customizable™ compared with SOC dressing in this clinical study.

As additional supportive analysis, the above analysis will be repeated based on the ITT population.

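### Does the SAP leave the primary significance level open between 0.05 and 0.048?

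*SAP*

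**What the plan says.** **Protocol.** Section 10.5.1 draws the favourable conclusion when the Customizable rate is lower and "the P-value from the above Fisher's Exact test is below 0.05". Section 10.1 reasons that, since "the purpose of the interim data review is not for any statistical comparison of effectiveness, no adjustment for multiplicity will be made". Section 10.8 adds: "There is no formal planned interim analysis for this clinical study". Section 10.7 says that departures from the planned methods will be documented in the SAP together with the "statistical rationale for diverting from the originally planned statistical summaries and/or analyses".

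**SAP.** Section 7.1 says that Fisher's test at a two-sided 0.048 "will be used to compare the SSC incidence rates between two treatment groups", and it repeats 0.048 in the decision rule. There the words ask for a p-value below 0.048, while the symbol allows equality. Section 10 repeats the protocol's statement on interim analysis, reports SSC rates of 17.2% (29 Customizable) and 3.1% (32 SOC), records the recommendation to terminate, and says that the 0.048 level "for statistical significance may be used for the primary analysis using the O'Brien-Fleming method". It gives no version of the method, no information fraction and no interim boundary. It refers to an interim data review plan, which is not among these documents and which may be included in the study report.

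**The concern.** Three statements seem to compete: 0.05 without adjustment, 0.048 as a firm level, and 0.048 as a possible level. The document containing the softest of them also shows the results by arm. A primary threshold left optional at that stage would let the analyst choose, with the data in view, whether a result counts as significant. A group-sequential level also sits oddly beside a protocol that planned no formal interim analysis and no adjustment, and the rationale that protocol 10.7 asks for is not written in the SAP. If the level really were open, the call on the primary endpoint could depend on that choice.

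**Working it through.** **1. Is 0.048 a real O'Brien-Fleming level?** For two looks with overall two-sided alpha 0.05 and information fraction *t* at the first look, the classic boundary *c* solves

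P(|Z1| > c/√t or |Z2| > c) = 0.05, with corr(Z1, Z2) = √t.

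At t = 0.50, c = 1.9774 and the final level is 0.0480, which reproduces the SAP's figure. The SAP gives no fraction, so the other choices below are assumptions:

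| Assumed fraction | Classic | Lan-DeMets, 0.025 per side | Lan-DeMets, 0.05 two-sided |
|---|---|---|---|
| 0.50 | 0.0480 | 0.0490 | 0.0478 |
| 60/102 (planned) | 0.0466 | 0.0478 | 0.0459 |
| 61/71 (realised) | 0.0428 | 0.0412 | 0.0386 |
| Interim alpha set at 60/102, final correlation √(61/71) | 0.0496 | 0.0498 | 0.0494 |

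The range is about 0.039 to 0.050. The SAP's value is recognisable, but its exact source cannot be read from the document. If the review spent no alpha, as protocol 10.1 intends, 0.048 is simply stricter than 0.05.

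**2. Counts behind the review rates (SAP 10).** 0.172 × 29 = 4.99, so 5/29. 0.031 × 32 = 0.99, so 1/32. The two-sided Fisher p-value is 0.093, in the direction against Customizable.

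**3. Tables the final analysis can reach.** SAP 5.2 reports "A total of 71 subjects", 36 Customizable and 35 SOC. Assume that the 61 reviewed subjects keep their status.
- Customizable can gain at most 36 − 29 = 7 subjects. For n = 29 to 36 there are 1 + 2 + … + 8 = 36 combinations of size and events.
- SOC can gain at most 35 − 32 = 3 subjects. For n = 32 to 35 there are 1 + 2 + 3 + 4 = 10 combinations.
- Total: 36 × 10 = 360 tables.

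Two of the 360 have 0.048 < p < 0.05: 6/30 v 1/32 (p = 0.0496) and 6/32 v 1/35 (p = 0.0481). Both have the higher rate on Customizable. At the full 36 v 35, no table falls between the levels.

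The lowest Customizable rate that can be reached is 5/36 = 13.9%, and the highest SOC rate is 4/35 = 11.4%. So no table has a lower rate on Customizable, and SAP 7.1's favourable conclusion cannot be drawn at any level.

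**4. If the deviation review removes subjects.** SAP 5.3 says: "Subjects having important disqualifying protocol deviations will be excluded from ITT and/or FAS". Remove up to K reviewed subjects, of any arm and outcome, then add new ones as in step 3:

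| K | Distinct tables | Between the levels | Lower rate on Customizable | Smallest p among those |
|---|---|---|---|---|
| 1 | 808 | 3 | 0 | none |
| 5 | 3,328 | 15, all against the device | 276 | 0.116 (0/31 v 4/35) |
| 10 | 7,994 | 30 | 1,020 | 0.0525 |

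A favourable table with p < 0.05 first appears at K = 11: 0/31 v 4/29, p = 0.0487. These are counts of tables, not probabilities.

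**5. Power under the design rates (35% v 8.75%).** Exact Fisher power at 44 per arm is 80.7% at 0.05, in line with the protocol's approximate 80%, and 80.4% at 0.048. At 36 v 35 it is 77.3% at both levels.

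**The case for a change.** The strongest case for acting is that the primary decision rule should be closed, above all once results by arm are known, and that an adverse finding is where discretion is least welcome. The two reachable tables between the levels are both adverse. Protocol 10.7 also called for a rationale, and the SAP offers only the name of a method. Had the review been a formal look at the realised fraction, 0.048 would be too generous (0.0428, 0.0412 or 0.0386).

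Part of this stands. The two verbs do not match, the rationale is not explicit, and the version and information fraction are missing. The mismatch between words and symbol in SAP 7.1 is also real.

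The rest does not carry a change. SAP 7.1 governs the primary analysis and states 0.048 without qualification. SAP 10 explains where the number came from and does not name 0.05 as an alternative. A later SAP may set a stricter level than the protocol. Placing 0.048 directly after the look by arm, with O'Brien-Fleming named, implies an adjustment for that look, and the interim data review plan may say more. The lenient-level argument assumes a formal efficacy look that the protocol did not plan, and under the assumptions of step 3 no level makes a favourable conclusion reachable.

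**Conclusion.** The concern does not call for a change. Reading SAP 10 as firm leaves the test at the 0.048 that SAP 7.1 already sets. Adding the version, fraction and rationale would supply detail without altering the analysis. The inequality is a clerical slip, and none of the computed p-values equals 0.048 exactly. SAP 5.4.1 already reports p-values to four decimals, so a reader can hold the result against either level. Going back to 0.05 would relax the threshold after the rates by arm were seen, with no gain.

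The size is 2 of 360 reachable tables, both against the device, and no effect on the conclusion that SAP 7.1 allows. This rests on counts inferred from rounded percentages, on the 61 reviewed subjects keeping their status, and on a final FAS no larger than 36 and 35. With up to five reviewed subjects removed, every table between the levels is still adverse. It takes 11 removals out of 61 before the choice of level could affect a favourable result.

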11. RANDOMIZATION RELEASE

As stated in the protocol,

“Subjects who meet all inclusion criteria and no exclusion criteria and who consent to participate in the study will be randomized in a 1:1 ratio to be treated with either Customizable or SOC surgical incision dressing. Due to the variances in complication rates between incision types, a stratified randomization will be used to ensure balance between the groups. The randomization will be stratified for each site and incision type of vertical/transverse and fleur-de-lis. Within each stratum, permuted blocks will be used to achieve equal numbers of Subjects assigned to Customizable or SOC surgical incision dressing. For each stratum, a randomization schedule will be generated to include Subject numbers and treatment assignments with the stratum of transverse/vertical incision starting with 1001 and the stratum of fleur-de-lis incision starting with 2001. Corresponding randomization envelopes will be prepared in sequential order by Subject number to provide randomization to each Investigator.

Randomization envelopes will be prepared corresponding to each row in the randomization schedule. Subject numbers will be printed and labeled clearly on the top of each envelope. Additionally, the envelopes will be color coded for incision type stratum, sealed, and organized by stratum and in ascending by Subject number.

Once the Subject has been screened, deemed eligible, and provided informed consent, the next available sequentially numbered randomization envelope within the corresponding stratum according to incision type; a sealed Customizable box and ActiV.A.C. unit will be taken into the operating room with the Subject. Randomization will be conducted in the operating room after closure of the surgical incision and confirmation of intra-operative eligibility. The envelope will be opened prior to surgical incision dressing placement and the assigned treatment arm will be

used. If Customizable is not selected, the sealed box and ActiV.A.C. unit will be returned to appropriate storage area.”

The randomization schedule for this study is a supplement to this statistical analysis plan and will be kept as a separate document.

Any deviation occurred during randomization process will be documented and corresponding actions/procedures will be followed. If a subject did not receive the assigned treatment by randomization, then the following actions will be performed:

1. Record the deviation in the protocol deviation file.
2. The subject will be analyzed according to actual treatment received in the Safety population.
3. The subject will be analyzed according to the randomized treatment in the ITT population.

12. QUALITY CONTROL/QUALITY ASSURANCE

Accurate, consistent, and reliable data will be ensured through the use of applicable KCI standard operating procedures, quality procedures, and work instructions.

All data listings, tables, and figures/graphs will be programmed using SAS Version 9.4 or later.
